8.3.2.4 ERROR PREDICTED REFRACTION (EPR)

The error predicted refraction (EPR) will be calculated for each treated eye as follows:

EPR = Postoperative MRSE adjusted to 6 meters – TRRE (target residual refractive error)

Then the absolute value of EPR will be derived. The means, standard deviations, minimum, and maximum of absolute EPR at each visit will be provided for all three lens cohort based on Implanted-eye Population. Additionally, the number and percentage of eyes with an EPR within ±0.50 D of target and of ±1.00 D of target will be derived for each postoperative visit.

For the HMIOL-eye Cohort and HMIOL Cohort 1, the difference in the absolute EPR between the HMIOL eye and its fellow eye at the same postoperative visits will be calculated for each subject. The mean, standard deviation, minimum, and maximum of the difference will be derived along with the 95% confidence interval of the mean difference.

For the HMIOL Cohort 2, the difference in the absolute EPR will be compared to the 3 month pre exchange EPR for the same eye at all postoperative visits. The mean, standard deviation, minimum, and maximum of the difference will be derived along with the 95% confidence interval of the mean difference.

[REDACTED]

9.0 DATA MANAGEMENT

9.1 DATA QUALITY ASSURANCE

All requested information must be entered on the eCRF and confirmable through source documentation. If an item is not available or not applicable, this fact should be clearly indicated.

Data will be entered into a computer database developed specifically for this trial. During the course of the trial, data queries will be generated for data points that are potentially erroneous and require appropriate clarification or correction.

9.1.1 DATA MONITORING

Periodic monitoring (either remote and/or on-site) will take place to ensure data integrity. Study monitoring involves the following elements:

CLARVISTA MEDICAL

PROTOCOL CP-00001 Rev.05

ClarVista personnel, or designee, may meet with investigators prior to the initiation of the study in order to review the adequacy of the subject population, facilities, and equipment with respect to the needs of the study, and to familiarize the investigator and support staff with the study protocol.

ClarVista personnel, or designee, may meet with the investigators at the time enrollment is initiated in order to ensure that subjects are being properly selected, that the methods described in the study protocol are thoroughly understood by the investigator, and that study data are being correctly recorded.

ClarVista personnel, or designee, may visit the clinical site at any time during the course of the study to review and/or collect completed case report forms. Additionally, telephone consultation will occur as necessary during the course of the study to ensure the proper progress and documentation of the study findings.

The study data will be carefully protected, and masking utilized to the extent possible, in order to prevent bias.

9.2 RECORD RETENTION

The investigator shall maintain all subject records for whichever of the following periods is shorter:

- A period of two years after the date on which FDA approves the marketing of the device
- A period of five years after the date on which the results of the study are submitted to the FDA in support of the marketing of the device

OR

- A period equal to the minimum required by the regional authority.

The Investigator / Site must contact ClarVista as provided in the Protocol Contacts page prior to discarding or disposing of any study related supplies or documents. The Sponsor retains the right to have all study documents shipped (at Sponsor's expense) for archival purposes, as an alternative to disposal.

Pachymetry ⁹	X					X	X	X	X	
IOP	X		X	X		X	X	X	X	
Pupil Size	X									
Lens Assessment	X									
Capsule Assessment ¹¹								X	X	
Dilated Fundus Exam	X		█	█		█	█	█	█	
Primary Surgery (HMIOL)		X								
Fellow Eye Surgery (see Table 2)										
Optic Exchange (see Table 3)										

² Assessments are to be completed for both eyes

³ Fellow Eye Consent - SOC

⁴ To include Urine Pregnancy Test if applicable

⁵ If UCDVA is < 20/40, perform Pinhole (PH) vision

⁶ Measurements via biometry will be utilized for both calculations and data capture

⁷ Measurement via biometry will be utilized for calculations

⁸ Measurement via Pentacam and submitted for assessment by the Reading Center

⁹ To be reviewed and approved by the Sponsor

¹⁰ Only for those subjects with planned Optic Exchange

APPENDIX A – TABLE 2: SCHEDULE OF ASSESSMENTS – FELLOW EYE

Table 2	Fellow Eye Cohort						
	Op-Visit 2 Fellow Eye Implant (Day 0 +7-30 Days)	Form 1.1 FE 1 Day Visit (Day 1-2)	Form 2.1 FE 1 Wk Visit (Day 7-14)	Form 3.1 FE 1 Mo Visit (Day 30-60)	Form 4.1 FE 3 Mo Visit (Day 80-100)	Form 5.1 FE 6 Mo Visit (Day 120-180)	Form 6.1 FE 12 Mo Visit (Day 330- 420)
Eligibility	X						
UCDVA		X	X	X	X	X	X
Manifest Refraction				X	X		X
BCDVA				X	X		X
[REDACTED]		■	■	■	■	■	■
[REDACTED]					X	X	X
Capsule Assessment						■	■
Dilated Fundus Exam					X		X
Fellow Eye Surgery	X						

APPENDIX A – TABLE 3: SCHEDULE OF ASSESSMENTS – COHORT 2

Table 3	Cohort 2 - Optic Exchange Complete						
	Op-Visit 3 Optic Exchange Visit (3 Mo Visit +1-21 Days)	Form 1.2 OE 1 Day Visit (Day 1-2)	Form 2.2 OE 1 Wk Visit (Day 7-14)	Form 3.2 OE 1 Mo Visit (Day 30-60)	Form 4.2 OE 3 Mo Visit (Day 80-100)	Form 5.2 OE 6 Mo Visit (Day 120-180)	Form 6.2 OE 12 Mo Visit (Day 330- 420)
Eligibility	X						
UCDVA ²³		X	X	X	X	X	X
Manifest Refraction			X	X	X	X	X
BCDVA			X	X	X	X	X
Keratometry ²⁴				X	X		X
Axial Length				X	X		X
[REDACTED]		■	■	■	■	■	■
Slit Lamp Examination		X	X	X	X	X	X
[REDACTED]					■	■	■
[REDACTED]					■	■	■
IOP		X	X	X	X	X	X
Lens / Capsule Assessment ²⁵					X	X	X
[REDACTED]		■	■	■	■		■
[REDACTED]		■	■	■	■		■
[REDACTED]		■	■	■	■		■
Dilated Fundus Exam					X		X
Optic Exchange Procedure	X						

²³ If UCDVA is <20/40, perform Pinhole (PH) vision

²⁴ Measurements via biometry

[REDACTED]

[REDACTED]	[REDACTED]	[REDACTED]
[REDACTED]	[REDACTED]	[REDACTED]
[REDACTED]	[REDACTED]	[REDACTED]
[REDACTED]	[REDACTED]	[REDACTED]
[REDACTED]	[REDACTED]	[REDACTED]

Date/Time (mm/dd/yyyy GMT):	Signed by:	Justification:
[REDACTED]	[REDACTED]	[REDACTED]
[REDACTED]	[REDACTED]	[REDACTED]

1 TITLE PAGE

Protocol Number:	ClarVista CP-00001
Medical Specialty:	Surgical
Project Name /Number:	NA
Sponsor Name & Address:	CLARVISTA MEDICAL, INCORPORATED [name] [name] [contact] [contact]
Test Article(s) / Product(s):	ClarVista HARMONI® Modular Toric Intraocular Lens System

Protocol CP-00001

ClarVista Medical, Inc.

Statistical Analysis Plan for Protocol CP-00001

Sponsor

ClarVista Medical, Incorporated
[name]
[name]
[contact]
[contact]

Original Version Date

24 February 2017

Protocol CP-00001

ClarVista Medical, Inc.

Table of Contents

1. Purpose	3
2. Scope.....	3
3. Software.....	3
4. Design and Objectives.....	3
5. Statistical Analyses.....	4
6. Sample Size	7
7. Analysis Populations	7
8. Sensitivity Analyses.....	8
9. Subgroup Analyses.....	8
	
11. Deviations from the Statistical Analysis Plan.....	9
12. References	9

Protocol CP-00001

ClarVista Medical, Inc.

1. Purpose

This Statistical Analysis Plan documents and describes the planned analyses for the CP-00001 CLEAR study. This is a feasibility study of the ClarVista HARMONI Modular Intraocular Lens System for the Treatment of Aphakia Following Cataract Surgery.

The intent of the study is to demonstrate the

- Feasibility of HARMONI IOL (HMIOL) implantation and assembly in subjects undergoing cataract surgery
- Feasibility of the HMIOL optic component exchange procedure (performed 3 months following primary cataract extraction)

Safety and effectiveness of these procedures will be characterized with the intent of supporting a future confirmatory study.

2. Scope

This document is based on the Investigational Plan CP-00001, Rev.05. Changes to the Investigational Plan may require updates to this document. Analyses described here expand on and supersede those described in the Investigational Plan.

3. Software

Statistical analyses will be performed with SAS System Software version 9.4 or above (SAS Institute, Cary, N.C.), R version 3.3 or above (R Core Team, <http://www.R-project.org>), or other validated statistical software package.

4. Design and Objectives

The CP-00001 study is designed as a prospective, multi-center, cohort study. Any pre-planned formal hypothesis tests for this feasibility study are not for the purposes of generating definitive conclusions to support regulatory approval.

Several cohorts of subjects are specified to help characterize the clinical significance of the study outcomes in eyes with and without optic exchange. These cohorts are defined as follows:

All HMIOL Eyes Cohort: Defined as all study eyes implanted with the study device. Analysis of follow-up visits for this cohort definition is restricted to 1 Day, 1 Week, 1 Month, and 3 Months following primary cataract extraction (PCE).

Cohort 1: Defined as the subset of study eyes implanted with the study device without a subsequent optic exchange procedure. Analysis of follow-up visits for this cohort definition is restricted to 1 Day, 1 Week and 1, 3, 6 and 12 Months following primary cataract extraction.

Cohort 2: Defined as the subset of study eyes implanted with the study device with a subsequent optic exchange procedure. Analysis of follow-up visits for this cohort will cover two time periods:

- Pre-Optic Exchange, comprising 1 Day, 1 Week, 1 Month, and 3 Months following primary cataract extraction, prior to the optic exchange visit.
- Post-Optic Exchange, comprising 1 Day, 1 Week, 1 Month, 3 Months, 6 Months, and 12 Months following optic exchange. The baseline for the post-optic exchange visits is the 3 Month pre-optic exchange visit.

Fellow Eyes Cohort: Defined as the contralateral eyes not implanted with the study device. Analysis of follow-up visits for this cohort definition is restricted to 1 Day, 1 Week, 1 Month, 3 Months, 6 Months, and 12 Months following primary cataract extraction.

Separate analyses are planned for each cohort.

Protocol CP-00001

ClarVista Medical, Inc.

5. Statistical Analyses

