8.3 STATISTICAL METHODS

The data analyses will be based on the analysis populations described above. No imputation for missing data will be performed. The statistical summaries will be prepared for HMIOL Cohort 1, HMIOL Cohort 2, and HMIOL eye Cohort (Cohort 1 + Cohort 2). For some selected outcomes, the summaries will be prepared for the fellow eye cohort.

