5.4. Safety Endpoints

All HMIOL Eyes Cohort

- [Redacted]
- [Redacted]
- Adverse event rates as compared to ISO 11979-7:2014 Annex B Safety and Performance Endpoint (SPE) tables including SSIs
- [Redacted]

Cohort 1 (No-Optic Exchange)

- [Redacted]
- AE rates as compared to ISO 11979-7:2014 Annex B Safety and Performance Endpoint (SPE) tables including SSIs
- [Redacted]

Cohort 2 (Optic Exchange)

- [Redacted]

Protocol CP-00001

ClarVista Medical, Inc.

A hypothesis test for this endpoint will be performed to assess whether mean percent change in ECC is no worse than 14%. The null and alternative are stated as:

$$H_0: \mu \geq 14\%$$

$$H_A: \mu < 14\%$$

Where μ represents the mean percent ECC loss from pre-exchange (3 months after the primary cataract surgery) to 3-month post-exchange for the eyes with HMIOL optic exchange (6 months after the primary cataract surgery). This test will be based on a one-sided, one-sample 0.05 t-test of a mean.

- [REDACTED]
- [REDACTED]
- AE rates as compared to ISO 11979-7:2014 Annex B SPE tables (includes SSIs –optic exchange procedures due to targeted residual refractive error are excluded)
- [REDACTED]

Fellow Eye Cohort

- [REDACTED]
- AE rates as compared to ISO 11979-7:2014 Annex B SPE tables including SSIs
- Dilated fundus examination

Adverse event rates in this study will be assessed as outlined in ISO 11979-7:2014 Annex B for posterior chamber IOLs. Following this methodology, for each specified adverse event we will calculate an exact lower one-sided 95% confidence bound for the proportion of eyes with the event at the one-year time point. As described in ISO 11979-7:2014 Annex B.3-B.4, success is defined as a lower bound that is less than the safety and performance endpoint (SPE) rate for that adverse event, in other words failing to reject the hypothesis that the event rate is greater than the SPE rate. The SPE rates for posterior chamber IOLs are provided in Table 1 below.

Table 1: Rates of Specific Adverse Events as Outlined in ISO 11979-7:2014 Annex B:

Adverse Event	Incidence Threshold
Cumulative	
Cystoid macular edema	3.0%
Hypopyon	0.3%
Endophthalmitis (inflammatory reaction (sterile or infectious) involving the vitreous body	0.1%
Lens dislocated from posterior chamber	0.1%
Pupillary block	0.1%
Retinal detachment	0.3%
Secondary surgical intervention (excluding posterior capsulotomies)	0.8%
Persistent	
Corneal stroma edema	0.3%

Protocol CP-00001

ClarVista Medical, Inc.

Cystoid macular edema	0.5%

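### SAP 4 ends All HMIOL Eyes analysis at 3 months, but SAP 5.4 lists that cohort's ISO adverse-event comparison and sets the bound at one year

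*SAP*

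**What the plan says.** **Visit limit.** SAP 4 defines the All HMIOL Eyes Cohort as all study eyes implanted with the device and says that analysis of its follow-up visits is "restricted to 1 Day, 1 Week, 1 Month, and 3 Months following primary cataract extraction (PCE". Cohorts 1 and 2 and the fellow eyes are carried to 12 months. SAP 4 adds: "Separate analyses are planned for each cohort".

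**SPE comparison.** Under All HMIOL Eyes, SAP 5.4 lists "Adverse event rates as compared to ISO 11979-7:2014 Annex B Safety and Performance Endpoint (SPE) tables including SSIs". After the cohort lists it gives the method: "we will calculate an exact lower one-sided 95% confidence bound for the proportion of eyes with the event at the one-year time point". That sentence names no cohort and excludes none. The SSI threshold in SAP Table 1 is 0.8%. Only the Cohort 2 entry carries the qualifier "optic exchange procedures due to targeted residual refractive error are excluded". The protocol's SSI endpoint (7.1) follows the same pattern, with planned exchanges excluded under Cohort 2 alone.

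**Protocol.** Section 8.3 defines the pooled group as "HMIOL eye Cohort (Cohort 1 + Cohort 2". Section 8.3.1.1 asks for the ISO events in that group at 12 months, counted from primary surgery in Cohort 1 and from the exchange in Cohort 2.

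**Precedence and status.** SAP 2 states: "Analyses described here expand on and supersede those described in the Investigational Plan". SAP 4 says that any formal tests are "not for the purposes of generating definitive conclusions to support regulatory approval".

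**BCDVA (protocol only).** Section 8.1 bases the 0.925 test on all HMIOL eyes, with Cohort 2 eyes taken after exchange. Section 8.3.2.1 gives the rule for the upper confidence limit but no decision visit for the pooled eyes.

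**The concern.** The same SAP stops the pooled cohort at 3 months and asks for a one-year SPE bound on it. Because both statements are in the SAP, its precedence over the protocol does not settle which one applies. The programmer would have to choose, and each literal choice gives a pooled result that is hard to use.

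- **At 3 months**, rates from the first 80 to 100 days are set against thresholds that the SAP applies at one year. Every optic exchange takes place after the 3 Month Visit, so the pooled rates say nothing about the exchange.
- **At one year**, the pooled SSI line has no visible rule for planned exchanges, and the SAP gives no time origin for one year in a group with two surgical dates.

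What is at stake is the pooled SPE bound, which is meant to inform the confirmatory study.

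**Working it through.** **1. Follow-up kept under the 3-month limit.** Inputs are the Appendix A windows: 3 Month Visit Day 80-100; exchange 1-21 days after that visit; 12 Month Visit Day 330-420 after primary surgery (Cohort 1) or after exchange (Cohort 2).

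- Cohort 1: 80/420 = 19% to 100/330 = 30% of one-year follow-up.
- Cohort 2, from Day 0: 80/(80 + 21 + 420) = 80/521 = 15% to 100/(100 + 1 + 330) = 100/431 = 23%. None of it is post-exchange.

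**2. Exposure at the protocol's pooled time point.** From Day 0, Cohort 2 is followed for 80 + 1 + 330 = 411 to 100 + 21 + 420 = 541 days, against 330 to 420 days in Cohort 1. The two cohorts therefore enter a pooled cumulative rate with different exposure.

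**3. How few SSIs exceed the threshold at one year.** The exact one-sided lower 95% limit L for x events in n eyes solves P(X ≥ x | n, L) = 0.05, which is the 5% quantile of Beta(x, n − x + 1). The threshold is 0.8% (SAP Table 1). The sizes are n = 105, the minimum enrolment in protocol 4.7.1, and n = 200, the enrolment ceiling.

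| Events / eyes | Observed | Lower limit | Above 0.8%? |
|---|---|---|---|
| 3 / 105 | 2.9% | 0.78% | no |
| 4 / 105 | 3.8% | 1.31% | yes |
| 4 / 200 | 2.0% | 0.69% | no |
| 5 / 200 | 2.5% | 0.99% | yes |

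For scale, protocol 4.7.1 pairs the 105 subjects with a minimum of 44 exchanges. If all 44 were counted as SSIs in the pooled line, the rate would be 44/105 = 42% (lower limit 34%). With 200 eyes and still 44 exchanges (assumed), it would be 44/200 = 22% (lower limit 17%). The documents do not say that they would be counted. The figures show only how far the result depends on the missing rule.

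**4. The BCDVA test.** Protocol 8.1 gives power 0.753 at n = 100, for H0 p ≥ 0.925, true p = 0.85 and one-sided 0.05. The exact binomial test rejects at 87 or fewer successes, and P(X ≤ 87 | 100, 0.85) = 0.753, so the figure is reproduced. It does not involve a visit and cannot show which one is meant. The time points that 8.3.2.1 names for the HMIOL-eye cohort are preoperative and 3 months after primary surgery, for the continuous summary. Both precede any exchange, so neither meets the post-exchange condition in 8.1.

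**The case against.** **The SAP can be read coherently.** The one-year sentence is general method text that follows the lists for all four cohorts. SAP 4 may limit only by-visit tables, or the one-year bound may be meant only for the cohorts carried to 12 months. The missing exchange exclusion under All HMIOL fits the second reading, since none is needed if analysis stops before any exchange. The SAP may also have narrowed the protocol's pooled analysis on purpose. These readings are possible, but the SAP states none of them, and it lists the SPE comparison under this cohort without qualification. The first still leaves the time origin and the SSI rule open. The second leaves the listed All HMIOL comparison with no stated time point for its bound.

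**Events are not lost.** A reader might infer that post-exchange harm drops out of the safety analysis. It does not. Cohorts 1 and 2 together cover the implanted eyes, and each has its own 12-month follow-up and SPE comparison. This objection stands.

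**BCDVA.** A reader might infer that the plan as a whole leaves the visit open. SAP 6 and the adjoining text are not visible in the public copy and may name it. In protocol 8.3.2.1 the sentence before the confidence limit reports percentages at every visit, so the limit may be intended by visit too. That would still give no decision visit for a group with two time origins. A reader might also infer that the pooled test gives way to two separate tests, or that the most favourable visit could be chosen. The sentence on separate analyses applies to the All HMIOL cohort as well, and nothing in the documents plans either approach.

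**Conclusion.** The wording conflict between SAP 4 and SAP 5.4 holds on the visible text, with high confidence. Followed literally, the 3-month limit yields a pooled SPE comparison without any post-exchange event. The one-year bound yields an SSI line with no visible rule for planned exchanges, where 4 events in 105 eyes or 5 in 200 are enough to exceed 0.8%. The event counts assume the enrolment minimum or ceiling with every eye in the denominator. The follow-up shares assume visits within the Appendix A windows.

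The BCDVA point is secondary, concerns the protocol text only, and carries low to moderate confidence.

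Severity is modest. The events remain visible by cohort, and the SAP disclaims definitive conclusions from its formal tests. The pooled bound should still be put right before analysis.

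**What to change.** 1. **SAP 4:** keep the by-visit All HMIOL tables to 3 months, say that the limit applies to those tables, and add a pooled final time point for the SPE comparison as in protocol 8.3.1.1.
2. **SAP 5.4:** refer the All HMIOL SPE bound to that time point. Apply the existing Cohort 2 exclusion of planned refractive optic exchanges to the pooled SSI line, and tabulate the exchanges separately.
3. **SAP 5.4:** show Cohort 2 events before and after exchange, because follow-up from Day 0 is longer there.
4. **Protocol 8.3.2.1:** unless the SAP text not visible here already does so, name one post-exchange visit for the pooled 0.925 BCDVA test before analysis, consistent with 8.1. The 12-month pooled time point is a natural candidate, but the documents do not state it and the choice is the sponsor's.

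The cost is a few sentences in SAP 4 and 5.4, at most one sentence in the protocol, and one pooled table with a before/after-exchange split. No new data or subjects are needed.

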Regulatory Status	Feasibility (Pre-IDE)
Investigational Device	ClarVista HARMONI™ Modular Intraocular Lens System, non-toric aspheric optic
Objectives	
 • To demonstrate the feasibility of HARMONI™ IOL (HMIOL) implantation and assembly in subjects undergoing cataract surgery. • To demonstrate the feasibility of the HMIOL optic component exchange procedure (performed 3 months following primary cataract extraction)
Number of Clinical Sites and Study Subjects	Up to 200 subjects will be treated in this study at up to 7 investigational sites. Enrollment will be monitored as outlined in Sample Size section and adjusted accordingly.
Study Duration	
All subjects will have up to 18 months study participation (Cohort dependent – see Study Design) from time of consent to study exit.
 
Total study duration will be approximately 24 months.

Study Design	
Prospective, multi-center clinical study.
 
All subjects will be seen for a Preoperative Visit to capture baseline measurements then undergo cataract surgery with primary eye (first implant) receiving a test lens (HMIOL). The investigator will determine if the test lens is to be implanted in OD or OS based on target refraction and the best interests of the subject.
 
Safety and Effectiveness testing of the HMIOL design allows the Investigator and Subject to decide if an optic exchange in the primary study eye is in the best interests of the subject based on refractive outcome and target. This determination will be made at the 3 month visit.
 
At the 3 Month Visit (post-primary cataract extraction), subjects with satisfactory (as determined by investigator and subject) outcomes in the study eye, or those opting not to pursue an optic exchange, will be entered into

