At the 3 month visit, an overall assessment of a subject's visual function will be performed by the physician. If the physician's assessment results in an opportunity for improved visual function through optic exchange in the test eye, the subject will be offered that opportunity. The Investigator and the Subject will decide if an optic exchange is appropriate.

The decision will be documented and the prospective Cohort indicated.

- If the subject has an acceptable outcome or it is otherwise decided an optic exchange will not take place, the subject will be entered into Cohort 1 and be followed at the 6 and 12 Month Visits prior to study completion. If the subject desires an exchange, however it is decided they cannot have one based on exclusion criteria (Section 3.2.4), the subject will remain in Cohort 1 and can utilize spectacles to correct RRE for the remainder of study participation. The investigator and subject can decide on further treatment per the Investigator's standard of care, following study participation.
- If it is decided an HMIOL optic exchange is desired, the appropriate pre-operative measurements will be obtained, 3 Month Visit assessments completed per Appendix A – Table 1, and HMIOL calculations and optic ordered. Finally, the subject will be scheduled for the procedure and entered into Cohort 2 (finalized after successful completion of optic exchange). If for any reason the optic exchange procedure does not take place, the subject will default back to Cohort 1.

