8.3.2.3 UCDVA

The LogMAR will be derived for UCDVA. The change in the LogMAR UCDVA from pre-optic exchange to post-optic exchange will be calculated for each of the HMIOL Cohort 2 eyes. The change will be summarized descriptively with the 95% confidence interval of the mean change at each post-optic exchange visit. The proportion of eyes with UCDVA of 20/20 or better, 20/25 or better, 20/32 or better, 20/40 or better, and

worse than 20/40 at each visit will be summarized for the HMIOL Cohort 2 at pre-exchange and every post-exchange visit. The difference in the proportions will be compared by McNemar test.

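### Cohort 2 change in UCDVA and absolute EPR is measured from the same 3 Month reading that leads to the exchange, so regression to the mean biases it toward improvement

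*SAP*

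**What the plan says.** **Selection.** The Protocol Synopsis (Study Design) has the investigator and subject "decide if an optic exchange in the primary study eye is in the best interests of the subject based on refractive outcome and target", and adds: "This determination will be made at the 3 month visit". Protocol 3.3.4 says that at this visit "an overall assessment of a subject's visual function will be performed by the physician", and that exchange is offered where this reveals "an opportunity for improved visual function through optic exchange in the test eye". No numeric threshold is given.

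**Baseline.** SAP section 4, under Cohort 2: "The baseline for the post-optic exchange visits is the 3 Month pre-optic exchange visit".

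**Analyses from that baseline.**
- UCDVA, Protocol 8.3.2.3: the within-eye change from before to after exchange. "The change will be summarized descriptively with the 95% confidence interval of the mean change at each post-optic exchange visit". For the acuity categories: "The difference in the proportions will be compared by McNemar test".
- Absolute EPR, Protocol 8.3.2.4: "the difference in the absolute EPR will be compared to the 3 month pre exchange EPR for the same eye", with a 95% interval for the mean difference. EPR is postoperative MRSE minus target, which is in substance the refractive outcome against target that drives the decision.

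SAP 5.1 also attaches a 95% interval to every change from an earlier visit and leaves p-values nominal. SAP section 8 plans no sensitivity analyses. The readable text has no repeat baseline, no adjustment for selection and no comparator for these changes.

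**The concern.** A measured value is a true value plus error. If eyes are picked because the measured value is poor, their errors are on average in the unfavourable direction. The next reading has fresh error, so the group mean moves back toward better with no treatment effect. Using the selecting reading as the baseline books that movement as benefit.

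Cohort 1 cannot act as the control, because it consists largely of eyes with satisfactory 3 Month outcomes and so is selected in the opposite direction.

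Two things are at stake. A 95% interval lying wholly on the improvement side should occur in 2.5% of trials when the exchange does nothing; here it would occur more often. And SAP section 1 says that the results are meant to support a future confirmatory study. An inflated exchange effect carried into that study's sample size would leave it underpowered.

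**Working it through.** The plan states no power, SD or expected change for these Cohort 2 analyses, so there is no figure to reproduce. The check sets the exchange effect to zero and asks what the planned analysis would show.

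**Inputs**
- Exchanged eyes: 44 (the minimum in Protocol 4.7.1), drawn from 105 (same section) or 200 (Protocol 3.1).
- Within-eye SD of MRSE: assumption. Treating the 0.50 D stability limit in inclusion criterion 6 as a 95% repeatability limit gives 0.50/(1.96 × √2) = 0.18 D.
- Within-eye SD of acuity: assumption. Treating the 10-letter limit in Protocol 6.1.1 (0.20 logMAR) the same way gives 0.20/(1.96 × √2) = 0.072 logMAR.
- Between-eye SD of EPR: assumption, 0.6 or 0.75 D. Protocol 1.0 cites about 0.6 D of residual error; 0.75 D follows if that is read as a mean absolute error.
- Between-eye SD of UCDVA: assumption, 0.15 logMAR, mean 0.12.
- Selection: pure (the 44 worst observed 3 Month values), or diluted by independent noise of SD τ for preference and other factors (0.6 D for EPR; 0.15 to 0.30 logMAR for UCDVA).

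**Hand check, UCDVA.** With selected fraction p = 44/N and selection intensity i = φ(z)/p, the expected spurious change is

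−i × σw² / √(σb² + σw² + τ²).

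Pure selection: σw² = 0.072² = 0.00518 and √(0.15² + 0.072²) = 0.166.
- N = 105: p = 0.419, i = 0.932; change = −0.932 × 0.00518/0.166 = −0.029 logMAR.
- N = 200: p = 0.22, i = 1.346; change = −1.346 × 0.00518/0.166 = −0.042 logMAR.

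The SE of the mean change is about √2 × 0.072/√44 = 0.0154. The chance that the interval shows improvement is about Φ(0.029/0.0154 − 1.96) = Φ(−0.07) = 47% and Φ(0.042/0.0154 − 1.96) = Φ(0.77) = 78%. Simulation (6,000 trials per case) gives the same 47% and 78%.

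**Simulation, absolute EPR, within-eye SD 0.18 D**

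| Between-eye SD | Drawn from | Selection | Mean change (D) | Interval shows improvement |
|---|---|---|---|---|
| 0.6 | 105 | pure | −0.070 | 45% |
| 0.6 | 200 | pure | −0.088 | 63% |
| 0.75 | 105 | pure | −0.058 | 32% |
| 0.75 | 200 | pure | −0.071 | 46% |
| 0.6 | 105 | diluted | −0.037 | 17% |
| 0.6 | 200 | diluted | −0.054 | 30% |
| 0.75 | 105 | diluted | −0.036 | 15% |
| 0.75 | 200 | diluted | −0.052 | 27% |

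Diluted selection for UCDVA gives mean changes of −0.014 to −0.031 logMAR and improvement in 14% to 53% of trials. With no selection on the value the rate is 2.7%, as it should be.

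**McNemar** (two-sided exact test at 0.05, assumed because the Protocol states no level). Chance of a significant improvement under pure selection:

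| Drawn from | 20/20 | 20/25 | 20/32 | 20/40 |
|---|---|---|---|---|
| 105 | 0.1% | 46.5% | 22.6% | 1.8% |
| 200 | 0% | 0.9% | 88.9% | 25.7% |

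The inflation falls on cuts near the edge of the selected group; elsewhere the test stays below nominal. The chance that at least one of the four cuts shows improvement is 60% to 92% under pure selection and 10% to 32% when diluted.

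**Alternative baseline.** With a second pre-exchange reading that played no part in selection, the mean change returns to about zero. The false-improvement rate is 2.2% to 2.3% for the UCDVA interval, 2.6% to 2.7% for the EPR interval, and at most 1.3% for any single UCDVA McNemar cut.

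If the decision instead uses the average of the 1 Month and 3 Month readings, both baselines are equally biased. With observed EPR SD 0.75 D and cut-offs from 0.5 to 1.0 D, either baseline shows improvement in 9% to 14% of trials at within-eye SD 0.15 D, and in about 17% to 31% at 0.25 D.

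**The case against.** The best case for leaving the plan alone has five parts.

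1. **Selection is softer than a cut-off.** The decision is an overall judgement shared with the subject, with opt-outs and clinical exclusions. This stands, and it is why the diluted range matters most. With a within-eye SD of 0.35 D and a hard cut-off, rates of 73% to 98% can be produced, but nothing in the documents supports that SD or such a rule.

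2. **Zero effect is an unlikely truth.** The exchange puts in an optic of different power, available in 0.50 D steps, so a spurious 0.04 to 0.09 D is small beside a real correction. As an illustration, if the exchange corrects the observed error with 0.3 D of residual scatter (an assumption), regression to the mean makes up about 5% to 8% of the apparent gain at within-eye SD 0.15 to 0.18 D. This stands as a limit on importance; the bias still has one direction.

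3. **Feasibility status.** SAP section 4 says that formal tests are not meant for definitive conclusions, the UCDVA change is called descriptive, and no readable success criterion rests on it. This lowers the consequence but does not remove the bias.

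4. **Pre-exchange visits are already tabulated.** SAP sections 4 and 9 present Cohort 2 before and after exchange, so a reader can compare 1 Month with 3 Month means. True, but no paired change from 1 Month is planned.

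5. **McNemar may no longer apply.** It is readable only in the Protocol, and the SAP says that its analyses supersede the Protocol's. Part of the SAP is not available here, so whether the test survives cannot be settled.

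A reader might extend the point to the endothelial cell test, which shares the baseline. The documents do not support that: eyes are not chosen for low counts, and unexplained cell loss counts against exchange (Protocol 3.2.4), so any regression there would work against the device.

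**Conclusion.** The concern holds for the UCDVA and absolute EPR changes in Cohort 2. Selection and baseline share one reading, and nothing in the readable plan corrects for it. The direction of the bias follows from the design. Its size rests on the assumed SDs and on how strongly the 3 Month value drives the decision.

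At a within-eye MRSE SD of 0.18 D, with 44 eyes and no exchange effect, the spurious absolute EPR gain is about 0.04 to 0.09 D. The interval shows improvement in roughly 15% to 30% of trials under diluted selection and 32% to 63% under pure selection, against 2.5%. For UCDVA the spurious change is about 0.01 to 0.04 logMAR.

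Three stronger readings do not follow. A reader might infer that the apparent benefit of exchange would be mostly artefact; a shift this small can create significance but cannot by itself account for a large correction. A reader might infer that every McNemar comparison is inflated; some cuts are and some are not. And a reader might take the 1 Month value to be free of selection error; that is so only to the extent that it did not inform the decision, and the documents do not say that it was ignored.

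This should be addressed, but it does not undermine the study.

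**What to change.** Keep the 3 Month baseline. In SAP sections 4 and 5.6, add a supplementary paired analysis of Cohort 2 change in UCDVA and absolute EPR, with 95% intervals, taking the 1 Month value after primary surgery as baseline. Add the McNemar comparison on the same basis if that test is retained. Whenever the size of the exchange benefit is stated, in particular for planning the confirmatory study, report the two results side by side.

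State in the SAP that the 1 Month baseline reduces the bias, and removes it only to the extent that the exchange decision did not also use the 1 Month data.

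No new visit is needed. Appendix A Table 1 marks UCDVA at 1 Month, and Protocol 8.3.2.4 already plans absolute EPR at each visit.

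The cost is a little extra analysis. The downsides are possible refractive drift between the 1 Month (Day 30-60) and 3 Month (Day 80-100) windows, which would enter the supplementary estimate, and a possibly smaller stated gain.
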